We will measure TNFR expression by B cells following immunization with PCV13 in 65-75 year old RT and compare them to each of the groups described in Specific Aim 1. Gene expression, with focus on the B cell activating factor (BAFF) system, will be measured in PPS-specific and non-PPS specific B cells using single cell genomics and flow cytometry. These measures will be correlated with post-immunization functional antibody activity, a surrogate of protection.

Our central hypothesis is that the aging RT population responds poorly to PCV13 vaccination reflecting the combined effects of aging and RT. We postulate that both the number of memory B cells and expression of tumor necrosis factor (TNF) superfamily receptors, which play crucial roles in the response to pneumococcal polysaccharides (PPS), are deficient in the elderly RT population and contribute to poor pneumococcal vaccine responses.

We have developed fluorescently labeled PPS allowing us to study the nature and surface receptors of PPS-specific B cells. Our preliminary data demonstrate that RT recipients 1. Respond poorly to pneumococcal immunization as measured by antibody titer and functional antibody activity. 2. RT recipients and healthy elderly have lower absolute number of both IgM and switched memory B cells. 3. The number of PPS-specific IgM and switched memory B cells are significantly lower in RT recipients and 4. TACI and BAFF-R, members of the TNF superfamily receptors, expression is significantly lower in the PPS-specific memory B cells in the RT population versus healthy controls. The overall objective of this proposal is to characterize the immune response and explore possible mechanisms of poor vaccine responsiveness following immunization with PCV in the rapidly growing group of elderly with RT. As the RT population is a

heterogeneous group we will study only those in whom the underlying cause of renal failure is diabetes mellitus type 2 (DM2) and/or hypertension (HTN).

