4.0 Study Endpoints (if applicable)

The primary endpoint of this study is: quantify the antibody titers in mg/mL and opsonophagocytic antibody titer calculated as serum dilution, number of polysaccharide specific B cells, and absolute number of cells/mL induced by vaccination with PCV13.

Secondary endpoint of the study is to describe differences in gene expression of 56 genes to be determined by single cell PCR and comparing these between groups.

The primary safety endpoint of the study is measured as minimal versus moderate local side effect. Minimal side effect measured as no impairment in activity. Moderate local side effect is a side effect affecting use of the extremity for less than 24 hours.

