The vaccine(s) administered to the participants are FDA approved vaccinations and vaccination protocols. The standard and recommended dose of vaccine will be administered either by a qualified nurse or physician and both vaccines are considered low risk. In groups 1-4 PCV13 will be administered per standard of care and is not part of the experimental protocol. In group 5, both PPV23 and PCV 13 are not routine part of care and are part of the experimental protocol. These vaccines have however been extensively studied in this and other populations and are considered low risk and 70-80% protective against pneumococcal disease [30].

The risk associated with blood draws is minimal.

The data to be collected will be stored using an excel spread sheet. The data include:

-cause of end stage kidney disease if applicable

Date of kidney transplant

Complete blood count (CBC), comprehensive chemistry profile including renal and liver functions, HbA1c, serum albumin as measure of nutrition, HbsAg, HCV and HIV test

Pre- and post-immunization serum antibody titers and opsonophagocytic antibody titers to PPS14, 19A and 23F in ug/mL

IgM and switched memory B cell number and percentage

PPS+ B cell number and percentage

Serum BAFF concentration

Gene expression of the genes listed below in Table 4

#	GENE SYMBOL	GENE TITLE	PROTEIN FUNCTION	#	GENE SYMBOL	GENE TITLE	PROTEIN FUNCTION
Apoptosis				Lymphocyte signaling			
1	Bcl-2	B-cell lymphoma 2	Apoptotic suppressor	30	CBLB	E3 ubiquitin-protein ligase	Negatively regulates B cell Ag receptor signaling
2	Bcl-Xl (BCL1)	B-cell lymphoma-extra large	Apoptotic suppressor	31	FCRL2	Fc receptor like 2	Expressed in memory B cells in humans
3	Mcl-1	Induced myeloid leukemia cell differentiation protein Mcl-1	Apoptotic suppressor	32	CD1D	CD1D	Antigen presentation
4	BAX	BCL2-associated X protein	Pro-apoptotic function	33	CD200	OX2 membrane glycoprotein	Controls inflammation; immunosuppression
5	BAD	BCL2-associated agonist of cell death	Pro-apoptotic function	34	LAIR1	Leukocyte associated immunoglobulin like receptor 1	Inhibitor of B cell mediated signaling
6	BIM (BCL11)	BCL2-interacting mediator of cell death	Pro-apoptotic function	35	CD72	B cell differentiation antigen CD72	Negative regulator of B cell responsiveness
7	FAS	Fas cell surface death receptor	Apoptosis signaling	36	RFTN1	Raft linking protein	B cell antigen receptor mediated signaling

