12.0 Data Management

Statistical Analysis Plan and Sample Size Justification for Aims 1 and 2

The primary outcomes in Aim 1 are serum antibody levels and functional antibody response measured using the OPA response at baseline and 30 days post-PVC₁₃ vaccine measured in the five groups defined in Table 1. The primary outcomes in Aim 2 are absolute number and proportion of B-cells phenotype specific to PPS₁₄, 19A, and 23F at baseline and 7 days post-PVC₁₃ vaccine measured in the same five groups. Comparisons between groups and within group between times for each aim will be evaluated using a linear

mixed model (LMM) approach. **The models will include fixed effects for participant group (65-75 RT, 35-45 RT, 65-75 DM/HTN, 65-75 healthy, and 35-45 healthy) and for time (day 0 or 30) and a random subject effect to account for repeated measures of antibody levels within participant.** Model assumptions will be checked graphically and transformations will be considered when necessary. Comparisons for each outcome between groups and within group between times will be evaluated using a series of contrasts from the LMM. **We are presenting power calculations for a range of assumptions to demonstrate that we anticipate having sufficient power to detect observed differences for all comparisons even if we fail to meet the recruitment target.** For power calculations we estimated the effect sizes for sample sizes ranging between 10 to 40 participants per group measured at 2 times at 80% and 90% power using a two-sided test assuming within subject correlation of 0.5 and Bonferroni adjusted and unadjusted significance

Figure 7: Effect sizes for different sample sizes, power, and significance

levels of $p = 0.005$ and 0.05 respectively. We will also evaluate the correlation between serum antibody levels and B cell count with OPA response across all participant groups using an LMM approach where OPA response is the dependent variable and antibody level or B-cell count is the independent variable. The model will include a random subject effect to account for repeated measures in the same subject. We anticipate good correlation (between 0.6-0.99), thus the objective is to estimate the correlation and define the level of precision around that correlation. A sample size of 200 subjects, 40 per group, provides >80% power to detect weak correlations of $r = 0.20$ and allows us to estimate a 95% confidence interval around the correlation to within ± 0.14 .

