Vaccination with the pneumococcal vaccine is linked with side effects that are usually considered minor side effects. In adults aged 18 years and older, the most commonly reported solicited adverse reactions (>5%) PCV13, or Prevnar were pain at the injection site (>50%), fatigue (>30%), headache (>20%), muscle pain (>20%), joint pain (>10%), decreased appetite (>10%), injection site redness (>10%), injection site swelling (>10%), limitation of arm movement (>10%), vomiting (>5%), fever (>5%), chills (>5%), and rash (>5%). The most common adverse reactions, reported in >10% of subjects vaccinated with PPV 23 or Pneumovax in clinical trials, were: injection-site pain/soreness/tenderness (60.0%), injection-site swelling/induration (20.3%), headache (17.6%), injection-site erythema (16.4%), asthenia and fatigue (13.2%), and myalgia (11.9%). Sometimes an allergic reaction can occur but this is very rare. The side effects are seldom more severe and may consist of fever, redness at the site of injection with lymph node swelling in the armpit which may last up to 3 days. This occurs rarely. It should be noted that pneumococcal vaccination (PCV13) is recommended for all RT recipients and all individuals >65 years of age where it is considered standard of care. All individuals in groups 1-4 will already have received PPV23 as part of their routine health care. Although both PPV23 and PCV13 vaccines are FDA approved, two vaccine regimen is not routine as standard of care in healthy HIV negative persons <65 although it is safe, so this vaccination is experimental in this use. Thus as healthy young control group, 35-45 years of age, an essential part in this study for comparator reasons, we will immunize with PPV23 a year before immunizing them with PCV13 so that all groups have received both PPV23 followed by PCV13. Again, a step absolutely necessary and safe, to generate interpretable data from this study.

All paperwork containing donor identifiable data is held in a locked file cabinet in the office of the PI. Each donor is assigned a random number and all samples resulting from that donor (blood, serum, cDNA) are labeled with that number. No donor identifiable data is used to mark samples. All staff who have completed appropriate IRB and HIPAA training and are aware of the importance of maintaining donor confidentiality.

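### No rule for OPA titres below the lowest dilution: if many day-0 sera lie there, the planned mixed model understates the rise to day 30, most in groups with low baselines

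*Combined protocol and SAP*

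**What the plan says.** Section 4.0 includes in the primary endpoint an "opsonophagocytic antibody titer calculated as serum dilution". The data list in section 10.0 gives a different scale: "Pre- and post-immunization serum antibody titers and opsonophagocytic antibody titers to PPS14, 19A and 23F in ug/mL".

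For Aim 1, section 12.0 names as primary outcomes "serum antibody levels and functional antibody response measured using the OPA response at baseline and 30 days" after PCV13, in five groups. The model has fixed effects for group and for time, and "a random subject effect to account for repeated measures of antibody levels within participant". No group-by-time term is listed. The plan then states: "Comparisons for each outcome between groups and within group between times will be evaluated using a series of contrasts from the LMM". On distribution it says only "Model assumptions will be checked graphically and transformations will be considered when necessary". OPA is also the dependent variable in the correlation models.

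The documents give no starting dilution, no detection limit, no value to record below it and no censored-data method.

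Two other statements bear on how often readings might fall below the limit. Section 1.0 reports from preliminary data that RT recipients "Respond poorly to pneumococcal immunization as measured by antibody titer and functional antibody activity". Section 15.0 states: "All individuals in groups 1-4 will already have received PPV23 as part of their routine health care". Group 5 is to have PPV23 about a year before PCV13.

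**The concern.** A dilution titre is left-censored at the first dilution tested. A laboratory usually records such a serum as the limit or half the limit, and the model then treats that number as a measurement. A log transformation leaves all these sera piled at one value, and that value then helps to set the group's baseline.

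The distortion is greatest on the day when titres are lowest. A group whose true baseline is near or below the limit is lifted at day 0 and much less at day 30, so its rise looks too small. If RT recipients start lower than their comparators, equal true rises can be read as a weaker RT response, which is the study's central hypothesis. The fill-in value is left open, so an unstated laboratory convention could move a primary result.

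**Working it through.** **The plan's own figures.** None concerns the floor. The neighbouring ones reproduce. Power for r = 0.20 with 200 subjects is Φ(atanh(0.20)·√197 − 1.96) = Φ(2.85 − 1.96) ≈ 0.81. The 95% half-width at r = 0 is tanh(1.96/√197) = 0.139. The Bonferroni level is 0.05/10 = 0.005. The power figure (Figure 7) is not shown and is not used here.

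**Inputs from the plan.** Day 0 and day 30; within-subject correlation 0.5; two-sided 0.05 and 0.005; 40 per group.

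**Assumptions not in the documents.** Log2 titre is normal with SD σ = 2; limit L = 0 on that scale; values below it recorded as half the limit (c = −1); true rise 3 log2 units (8-fold) in every group; control baseline mean 2; RT baseline mean 1, 0 or −1. Titres are simulated as continuous, not stepped.

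**Mean recorded log2 titre** for true mean μ, with a = (L − μ)/σ:

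M(μ) = c·Φ(a) + μ·[1 − Φ(a)] + σ·φ(a)

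*RT, baseline μ = −1.* Day 0: a = 0.5, M = −0.691 − 0.309 + 0.704 = −0.296. Day 30 (μ = 2): a = −1, M = −0.159 + 1.683 + 0.484 = 2.008. Recorded rise 2.304, or 2^2.304 = 4.9-fold against a true 8-fold.

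*Control, baseline μ = 2.* Day 0: 2.008. Day 30 (μ = 5): 4.998. Recorded rise 2.990, or 7.9-fold.

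| Share below limit at day 0 | Recorded rise, half-limit | Recorded rise, limit |
|---|---|---|
| 16% (control) | 7.9 | 7.2 |
| 31% | 7.5 | 6.2 |
| 50% | 6.5 | 4.8 |
| 69% | 4.9 | 3.4 |

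**False-positive rate for RT versus control difference in rise** (simulated two-sample test of change, which for two complete time points is the group-by-time contrast; half-limit; control share 16%):

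| RT share below limit | 40 per group, 0.05 | 40 per group, 0.005 | 55 per group, 0.05 |
|---|---|---|---|
| 31% | about 5% | 0.6% | about 5% |
| 50% | about 11% | 1.6% | 12% |
| 69% | about 35% | 11% | 46% |

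The 55 is section 6.0's 275 divided by 5. Recording the limit itself, at 40 per group and 0.05, gives about 8%, 30% and 77%. With equal baselines the rate is nominal (5.1% in a run with a true 4-fold rise).

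**Level contrasts in the same 69% case** (true gap 3.0 log2). Day 30: 4.998 − 2.008 = 2.99. Day 0: 2.008 − (−0.296) = 2.30. Average of the two days: 2.65. With the limit as fill-in, day 30 gives 2.84 and the average 2.30. The floor leaves these gaps about right or makes them smaller.

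**Does censoring repair it?** A left-censored random-intercept model was tried with a true 4-fold rise, limit at titre 8, control baseline geometric mean 32 and RT baseline 4 or 2. The RT/control ratio of rises was 1.05 and 1.07 (truth 1.00), against 0.55 and 0.43 for the plain model with the limit as fill-in. Its false-positive rates were 6.5% and 9.5% at 0.05, and 2.0% and 1.5% at 0.005. With only 200 runs these are imprecise, but they suggest a slightly liberal test.

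**The case against.** A reader might infer that the floor biases the whole OPA analysis toward the central hypothesis. The documents do not support that. Section 12.0 does not name fold-rise as the OPA estimand and lists no group-by-time term. The group contrast in the model as listed averages over days, and there the floor works against the hypothesis; at day 30 it is close to neutral. The direction toward the hypothesis holds only for differences in rise between groups.

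A reader might also infer that the preliminary data show RT recipients at the floor on day 0. Section 1.0 reports a poor response to immunization, not a low baseline titre, and no baseline OPA is given for any group. PPV23 is planned to precede PCV13 in every group, which may lift baselines off the floor. Without a lower RT baseline there is no differential bias.

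Both objections stand. So does the remark that limit, SD, true rise, shares below the limit and fill-in value are all assumed: the 35% needs an 8-fold lower RT baseline, and at 31% below the limit the rate is essentially nominal. With half-limit fill-in and few low values, the rise can even be slightly overstated (8.15 against 8 at 9% below the limit and SD 1.5).

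The gap itself remains. The plan does intend within-group contrasts between days, and these are understated when many day-0 sera are below the limit. Nothing says how such sera will be recorded or analysed.

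**Conclusion.** The point holds as a conditional one. The plan treats a left-censored primary outcome as fully measured, and its only remedy cannot recover the lost values. If a substantial share of day-0 sera lie below the lowest dilution, within-group rises are understated, and groups with lower true baselines can falsely show a smaller rise. Level comparisons between groups are nearly unbiased at day 30 or conservative when averaged over days.

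Under the stated assumptions a true 8-fold rise reads as 7.5, 6.5 or 4.9-fold at 31%, 50% or 69% below the limit. The matching false-positive rates at 0.05 are about 5%, 11% and 35% with 40 per group. They illustrate the mechanism and do not forecast this trial; few low readings or equal baselines would make the differential effect negligible. Low readings would also enter the correlation models with OPA as dependent variable, but no direction or size has been worked out for that.

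**What to change.** In section 12.0, for OPA:

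- State the starting dilution and the limit, and reconcile the OPA units between sections 4.0 and 10.0.
- Analyse log titre with a mixed model that treats values below the lowest dilution as left-censored (a Tobit mixed model).
- Add a group-by-time term, so that rises can be compared between groups and the within-group contrasts can differ by group.
- Report the share below the limit by group and day.
- Repeat the analysis with the limit and with half the limit as fixed fill-in values, labelled as sensitivity analyses.

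The cost is plan wording and slightly more analysis work; no new data are needed. The downside is that the censored model leans on log-normality when most of a group is below the limit. The fill-in analyses and the reported shares let a reader see when that is the case.

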Accordingly, pneumococcal vaccination is recommended for all adults ≥ 65 years of age and all RT recipients [12, 13]. In 2012 the vaccination recommendations by the Advisory Committee on Immunization Practices (ACIP) for these immune compromised adults, were changed to include vaccination with the 13-valent pneumococcal conjugate vaccine (PCV13) [12]. Although highly successful in infants, immunogenicity studies have overall failed to demonstrate superiority of PCV based regimens in older adults [14]. Similarly, a prime-boost regimen based on sequential immunization with PCV7 and the 23-valent pneumococcal polysaccharide vaccine, Pneumovax[®] (PPV23), has not demonstrated improved responses in RT and liver transplant populations [6, 7]. The RT population ≥ 65 years of age is rapidly growing and represents a unique subpopulation with combined immunodeficiencies related to aging [15] and immunosuppressive drugs related to transplant. Both aging and RT result in a marked increased risk of pneumococcal disease with decreased immune response to pneumococcal vaccination. The immune response to vaccination with PCV is poorly characterized in the aging and transplant populations, and may not be more effective than PPV23 alone, implying the need for alternate vaccine/adjuvant strategies. Moreover, studies characterizing and comparing antigen-specific B cell responses in well-defined RT populations are lacking.

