16.0 Potential Benefits to Subjects or Others

The benefits of participation in the study will consist of;

1. Individual benefit: The protection offered by the vaccination protocol is thought to be beneficial to each participant although the degree of protection will vary from person to person. Pneumococcal vaccination is however recommended to all over 50 years of age and some studies show that the addition of PCV13 is beneficial and results in a better protection against pneumonia. The majority of the participants will receive PCV13 regardless of participation in the study as this is part of standard of care for individuals in groups 1-4. The vaccine costs in group 1-4 will be charged to the patient's insurance as pneumococcal vaccination is standard of care.
2. The ultimate goal of the study is to define the degree of protection against pneumococcal disease induced by the pneumococcal conjugate 13 valent vaccine in the aging RT population. Does the a The experimental data, i.e. antibody titers, opsonophagocytic titers, B cell characteristics and single cell PCR results will be stored on laboratory computers and individual notebooks however this data will only be identified by numerical identifier. NO patient identifiers will be used on laboratory specimen or data at ANY time during the study. All experimental data will be confirmed by performing each experiment in duplicate. All computers require ID specific log-in. At no time is patient information associated with the data except at the time of analysis by the investigator if additional clinical information is needed. The results of the study will clarify and increase our understanding of both the aging and young RT recipients and particularly identify the potential cause of poor or deficient responses. The results of these studies may benefit not only the 20% of the RT population over 65 years of age but also the younger RT recipients.

The risks involved in this study are truly minimal and therefore based on the potential personal benefit to the enrolled volunteers and the overall knowledge gained, reasonable.

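### The OPA correlation is pooled over five groups with no group term, so it combines the transplant gap with any individual-level link; a group-adjusted correlation should be reported beside it

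*Combined protocol and SAP*

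**What the plan says.** The analysis plan for Aims 1 and 2 (Section 12.0) describes two kinds of model. The comparison models list fixed effects for the five groups and for time. The correlation analysis is then specified separately: "We will also evaluate the correlation between serum antibody levels and B cell count with OPA response across all participant groups using an LMM approach". OPA is the outcome, antibody level or B-cell count is the single independent variable, and "The model will include a random subject effect to account for repeated measures in the same subject". Neither a group nor a time term is listed. The purpose is estimation: "We anticipate good correlation (between 0.6-0.99), thus the objective is to estimate the correlation". The plan claims more than 80% power for r = 0.20 with 200 subjects, 40 per group, and a 95% CI within ±0.14.

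Among the preliminary findings in Section 1.0, RT recipients "Respond poorly to pneumococcal immunization as measured by antibody titer and functional antibody activity", and "The number of PPS-specific IgM and switched memory B cells are significantly lower in RT recipients". Specific Aims 2 and 3 tie the B-cell measures to OPA after vaccination. Under the blood-sample timing in Section 10.0, flow cytometry uses day 0 and day 7 (the RT time point may be revised to day 5 or 10), and antibody and OPA use day 0, day 30 and yearly samples. Section 12.0 does not say which time points enter the antibody–OPA correlation.

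**The concern.** Two of the five groups are expected to be lower on both variables being correlated. Pooling them with three groups that are not creates a positive association even if, inside each group, people with more PPS-specific B cells do not make more functional antibody. Section 2.0 names something that could lower both at once, describing older RT recipients as having "combined immunodeficiencies related to aging [15] and immunosuppressive drugs related to transplant".

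The random subject effect handles repeated values from one person. It does not condition on group: the mixed-model slope is a weighted mix of within-subject and between-subject association, and the between-subject part contains the group gap.

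At stake is what the figure can be used for. The central hypothesis in Section 1.0 is that memory B-cell numbers and receptor expression "are deficient in the elderly RT population and contribute to poor pneumococcal vaccine responses", and Section 16.0 hopes to "particularly identify the potential cause of poor or deficient responses". From the pooled correlation alone, a reader cannot tell an individual-level link from transplant groups simply being lower on both measures.

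**Working it through.** **Inputs from the plan.** n = 200, 40 in each of 5 groups, 2 of them RT; r = 0.20; anticipated r of 0.6 to 0.99. The correlation text gives no significance level, so two-sided 0.05 is assumed.

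**Inputs assumed.** The documents give no RT gap in SD units. A gap D of 0.5 to 2 within-group SD is used as a range.

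**1. The plan's own figures.** Fisher z, one value per subject, k covariates:
- Power = Φ(atanh(r)·√(n − k − 3) − 1.96). With k = 0: 0.2027 × √197 = 2.845; 2.845 − 1.96 = 0.885; power 81.2%.
- Largest CI half-width, at r = 0: tanh(1.96/√197) = 0.139.

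Both agree with the stated figures.

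**2. Pooled r with the same gap on both variables.** The RT indicator has variance 0.4 × 0.6 = 0.24. With within-group SD 1 and within-group correlation ρ:

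pooled r = (ρ + 0.24D²)/(1 + 0.24D²)

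| D (SD) | 0.24D² | pooled r, ρ = 0 | pooled r, ρ = 0.6 |
|---|---|---|---|
| 0.5 | 0.06 | 0.06 | 0.62 |
| 1 | 0.24 | 0.19 | 0.68 |
| 1.5 | 0.54 | 0.35 | 0.74 |
| 2 | 0.96 | 0.49 | 0.80 |

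With no individual link, a 1 SD gap alone gives about the r = 0.20 that the plan is powered to detect. In simulation (3,000 runs, ρ = 0), the pooled r reached p < 0.05 in 12.6%, 79.0%, 100% and 100% of runs for the four gaps; with group adjustment it did so in 4.4 to 5.6%.

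**3. What the equal-gap scenario implies.** If B cells explain ρD of the OPA gap, the remaining D(1 − ρ) is an RT effect on OPA that does not pass through B cells: 0.4 SD at ρ = 0.6 and D = 1, and the whole gap at ρ = 0.

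**4. The alternative: the OPA gap runs wholly through B cells.** The B-cell gap is then D and the OPA gap ρD.
- Pooled slope = ρ(1 + 0.24D²)/(1 + 0.24D²) = ρ, equal to the within-group slope.
- Pooled r = ρ√(1 + 0.24D²)/√(1 + 0.24ρ²D²). At ρ = 0.6, D = 1: 0.6 × √1.24/√1.0864 = 0.64.

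If only one variable is lower by 1 SD, pooled r falls instead: 0.6/√1.24 = 0.54. Upward distortion needs both to be lower, as Section 1.0 reports.

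**5. Does the random subject effect help?** The listed mixed model was simulated with three serotypes pooled, post-vaccination values, within-subject correlation 0.5 and ρ = 0 (1,000 runs). Pooling the serotypes is an assumption; the plan does not say. For gaps of 0.5, 1, 1.5 and 2 SD:
- As listed: mean slope 0.03, 0.09, 0.16, 0.24; p < 0.05 in 9.9%, 61.6%, 97.3%, 100%.
- With group terms: mean slope −0.003 to 0.002; p < 0.05 in 4.4 to 5.8%.

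The random effect dampens the mixing but does not remove it.

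**6. Time, only if day 0 and day 30 both enter the antibody–OPA model.** With no group gap and no individual link, an assumed shared rise of 0.5, 1 or 2 SD gives a mean slope of 0.11, 0.29 or 0.63. With group, time and group-by-time terms it is −0.002 to 0.002.

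**7. Cost of adjustment.** With k = 4, power for r = 0.20: 0.2027 × √193 = 2.816; 2.816 − 1.96 = 0.856; 80.4%. Largest half-width: tanh(1.96/√193) = 0.140. At r = 0.6 the half-width goes from 0.089 to 0.090.

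**The case against.** **Estimation is the stated aim, and the causal wording sits elsewhere.** This stands. The hypothesis in Section 1.0 is a postulate and the phrase in Section 16.0 belongs to the benefits text; neither is attached to this model. A reader might infer that the plan draws a causal conclusion from the pooled correlation, or that the correlation is invalid. The documents support neither. But an estimate still needs a defined target, and pooled and within-group correlations are different targets.

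**Group may lie on the hypothesised pathway.** This also stands. If transplantation lowers B cells and so lowers OPA, the between-group gap is part of the signal, and adjustment removes it. A reader might conclude that only the adjusted figure may inform mechanism. That is too strong: in step 4 the pooled slope is exactly right.

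**The plan anticipates r of 0.6 or more, where the shift is small.** This holds only in part. At ρ = 0.6 and gaps up to 1 SD, the shift of 0.02 to 0.08 is inside the CI half-width of 0.09. At 1.5 and 2 SD it is 0.14 and 0.20, which is outside.

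**The sentence listing group fixed effects could cover this model too.** This is the weaker reading. That sentence belongs to the comparison models, and the correlation model then lists its own terms. At the least the text needs clarifying.

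**Conclusion.** The concern holds, as a minor one. As written, the OPA correlation combines the gap between RT and non-RT groups with any association among individuals, and no planned analysis separates the two. The size cannot be fixed from the documents. It depends on the unknown gap and on how much of the OPA gap passes through B cells: from no distortion of the slope if all of it does, to a pooled r of 0.19 at 1 SD or 0.49 at 2 SD from group differences alone if none does. The assumed gap is confined to the two RT groups; Section 1.0 also reports fewer memory B cells in healthy elderly, so the group terms should cover all five groups.

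The pooled correlation stays a legitimate planned result, the stated power and precision are reproduced, and the primary group and time comparisons, which have their own group and time terms, are not affected.

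**What to change.** Keep the pooled correlation and add beside it a group-adjusted (within-group) correlation with its 95% CI:

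- Use post-vaccination values: the post-vaccination B-cell sample, or day-30 antibody, with day-30 OPA.
- Include four group terms for the five groups.
- Name the estimator for both figures. Either run the analysis per serotype with one value per subject, as a partial correlation needing no random effect, or state that serotypes are pooled with a random subject effect.
- If day 0 and day 30 both enter the antibody–OPA model, add time and group-by-time.
- Interpret both figures. Call the association individual-level only if it is also seen in the adjusted estimate, and note that adjustment removes any between-group part of the pathway.

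The cost is analysis-plan wording and four parameters, with no extra subjects. The power and precision figures in step 7 apply to one value per subject, and the stated 80% and ±0.14 are still met. The adjusted correlation may be smaller than the pooled one.
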